## 6.13.3.3.2. Severe Gastrointestinal Events

Severe gastrointestinal (GI) adverse events will be captured with AE-CRF form and serious cases will be captured with the SAE form. The PTs in the GI SOC MedDRA version at the time of database locks will be used to identify GI AEs, and only the PTs with serious/severe treatment-emergent cases will be considered as AESIs.

The counts and percentages of participants with severe/serious treatment-emergent GI events will be summarized by treatment.

### 6.13.3.4. Hepatic Safety

## 6.13.3.4.1. Hepatobiliary Disorders

Hepatobiliary disorders will be considered as AESI. The counts and percentages of participants with treatment-emergent potentially drug-related hepatic disorders will be summarized by treatment using the MedDRA PTs. Detailed searching criteria can be found in Appendix 1.

A listing of participants with treatment emergent hepatobiliary disorders may be provided if deemed necessary.

### 6.13.3.4.2. Liver Enzymes

Analyses for laboratory analyte measurements are described in Section 6.13.6. This section describes additional analyses of liver enzymes.

The counts and percentages of participants with the following elevations in hepatic laboratory tests at any time during the treatment period and during the entire study including follow up period will be summarized between treatment groups:

- The counts and percentages of participants with an alanine aminotransferase (ALT) measurement ≥3 times (3x), 5 times (5x), and 10 times (10x) the Covance ULN will be summarized for all participants with a postbaseline value and for subsets based on various levels of baseline value.
  - participants whose nonmissing maximum baseline value is ≤1x ULN
  - $\circ$  participants whose maximum baseline is >1x ULN, and
  - participants whose baseline values are missing.
- The counts and percentages of participants with an aspartate aminotransferase (AST) measurement ≥3x, 5x, and 10x the Covance ULN during the treatment period will be summarized for all patients with a postbaseline value and for subsets based on various levels of baseline, as described above for ALT.
- The counts and percentages of participants with a total bilirubin (TBL) measurement ≥2x the Covance ULN during the treatment period will be summarized for all participants with a postbaseline value, and subset into 4 subsets:
  - participants whose nonmissing maximum baseline value is  $≤1 \times ULN$
  - $\circ$  participants whose maximum baseline is >1 x ULN, but <2 x ULN
  - $\circ$  participants whose maximum baseline value is  $\geq 2 \times ULN$ , and
  - o participants whose baseline values are missing.
- The counts and percentages of participants with a serum alkaline phosphatase (ALP) measurement ≥2x the Covance ULN during the treatment period will be summarized for all participants with a postbaseline value and for the subsets described above to TBL.

Maximum baseline will be the maximum non-missing observation in the baseline period. The maximum value will be the maximum non-missing value from the postbaseline period. Planned and unplanned measurements will be included.

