A psychiatrist or appropriately trained professional may assist in the decision to discontinue the participant.

• Discontinuation due to a hepatic event or liver test abnormality.

- Participants who are discontinued from investigational product due to a hepatic event or liver test abnormality should have additional hepatic safety data collected via eCRF.
- O Discontinuation of the investigational product for abnormal liver tests **should be** considered by the investigator when a participant meets one of the following conditions after consultation with the Lilly designated medical monitor:
 - ALT or AST >8x ULN
 - ALT>2x baseline value OR ≥300U/L, whichever occurs first, if baseline ALT≥2x ULN
 - ALT or AST >5x ULN for more than 2 weeks
 - ALT or AST >3x ULN and TBL >2x ULN or international normalized ratio (INR) >1.5
 - ALT or AST >3x ULN with the appearance of fatigue, nausea, vomiting, right upper-quadrant pain or tenderness, fever, rash, and/or eosinophilia (>5%)
 - ALP > 3x ULN
 - ALP >2.5x ULN and TBL >2x ULN
 - ALP >2.5x ULN with the appearance of fatigue, nausea, vomiting, right quadrant pain or tenderness, fever, rash, and/or eosinophilia (>5%)

Participants who stop the study drug permanently should continue to attend all scheduled study visits to collect all planned efficacy and safety measurements. Participants who are unwilling to attend all scheduled visits and stop the study prior to 52 weeks, should return for a final weight measurement (Visit 99). If participants are unwilling to attend visit 99, their refusal to attend should be documented in the patient medical record.

Participants discontinuing from the investigational product prematurely for any reason should complete adverse event and other follow-up procedures per Section 2 (Schedule of Activities), Section 9.2 (Adverse Events), and Section 9.4 (Safety) of this protocol.

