9.4.6. Safety Monitoring

9.4.6.1. Hepatic Safety Monitoring

9.4.6.1.1. Close Hepatic Monitoring

Laboratory tests (Appendix 2), including ALT, AST, ALP, TBL, direct bilirubin (D. Bil), gamma-glutamyl transferase (GGT), and creatine kinase (CK), should be repeated within 48 to 72 hours to confirm the abnormality and to determine if it is increasing or decreasing, if one or more of these conditions occur:

If a participant with baseline results of:	develops the following elevations:
ALT or AST <1.5x ULN	ALT or AST ≥3x ULN
ALP <1.5x ULN	ALP ≥2x ULN
TBL <1.5x ULN	TBL ≥2x ULN (except for patients with Gilbert's syndrome)
ALT or AST ≥1.5x ULN	ALT or AST ≥2x baseline
ALP ≥1.5x ULN	ALP ≥2x baseline
TBL ≥1.5x ULN	TBL ≥1.5x baseline (except for patients with Gilbert's syndrome)

Abbreviations: ALT = alanine aminotransferase; ALP = alkaline phosphatase; AST= aspartate aminotransferase; TBL = total bilirubin; ULN = upper limit of normal.

If the abnormality persists or worsens, clinical and laboratory monitoring, and evaluation for possible causes of abnormal liver tests should be initiated by the investigator in consultation with the Lilly-designated medical monitor. At a minimum, this evaluation should include physical examination and a thorough medical history, including symptoms, recent illnesses (for example, heart failure, systemic infection, hypotension, or seizures), recent travel, history of concomitant medications (including over-the-counter), herbal and dietary supplements, history of alcohol drinking and other substance abuse.

Initially, monitoring of symptoms and hepatic biochemical tests should be done at a frequency of 1 to 3 times weekly, based on the participant's clinical condition and hepatic biochemical tests. Subsequently, the frequency of monitoring may be lowered to once every 1 to 2 weeks, if the participant's clinical condition and lab results stabilize. Monitoring of ALT, AST, ALP, and TBL should continue until levels normalize or return to approximate baseline levels.

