9.4.6.1.2. Comprehensive hepatic evaluation

A comprehensive evaluation should be performed to search for possible causes of liver injury if one or more of these conditions occur:

If a participant with baseline results of	develops the following elevations:
ALT or AST <1.5x ULN	ALT or AST ≥3x ULN with hepatic signs/symptoms*, or
	ALT or AST ≥5x ULN
ALP <1.5x ULN	ALP ≥3x ULN
TBL <1.5x ULN	TBL ≥2x ULN (except for patients with Gilbert's syndrome)

ALT or AST ≥1.5x ULN	ALT or AST ≥2x baseline with hepatic signs/symptoms*, or ALT or AST ≥3x baseline
ALP≥1.5x ULN	ALP ≥2x baseline
TBL ≥1.5x ULN	TBL ≥2x baseline (except for patients with Gilbert's syndrome)

^{*} Hepatic signs/symptoms are severe fatigue, nausea, vomiting, right upper quadrant abdominal pain, fever, rash, and/or eosinophilia >5%.

Abbreviations: ALT = alanine aminotransferase; ALP = alkaline phosphatase; AST= aspartate aminotransferase; TBL = total bilirubin; ULN = upper limit of normal.

At a minimum, this evaluation should include physical examination and a thorough medical history, as outlined above, as well as tests for prothrombin time-international normalized ration (PT-INR); tests for viral hepatitis A, B, C, or E; tests for autoimmune hepatitis; and an abdominal imaging study (for example, ultrasound or computer tomography [CT] scan).

Based on the patient's history and initial results, further testing should be considered in consultation with the Lilly-designated medical monitor, including tests for hepatitis D virus (HDV), cytomegalovirus (CMV), Epstein-Barr virus (EBV), acetaminophen levels, acetaminophen protein adducts, urine toxicology screen, Wilson's disease, blood alcohol levels, urinary ethyl glucuronide, and serum phosphatidylethanol. Based on the circumstances and the investigator's assessment of the participant's clinical condition, the investigator should consider referring the participant for a hepatologist or gastroenterologist consultation, magnetic resonance cholangiopancreatography (MRCP), endoscopic retrograde cholangiopancreatography (ERCP), cardiac echocardiogram, or a liver biopsy.

9.4.6.1.3. Additional hepatic data collection (hepatic safety CRF) in study participants who have abnormal liver tests during the study

Additional hepatic safety data collection in hepatic safety case report forms (CRF) should be performed in study participants who meet 1 or more of the following 5 conditions:

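### The planned liver tables take one analyte at a time, so no by-arm count shows how many participants meet the enzyme-plus-bilirubin patterns in Protocol 8.1.1 (minor, cheap to add)

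*SAP*

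**What the plan says.** Protocol Section 8.1.1 lists eight liver-test conditions under which the investigator should consider stopping study drug, after consulting the sponsor's medical monitor. Two of them pair an enzyme with bilirubin:

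- "ALT or AST >3x ULN and TBL >2x ULN or international normalized ratio (INR) >1.5", read here as the aminotransferase rise together with either the bilirubin rise or the INR rise;
- "ALP >2.5x ULN and TBL >2x ULN".

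SAP Section 6.13.3.4.2 is the dedicated liver-laboratory section. It plans by-arm counts and percentages for the treatment period and for the whole study including follow-up:

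- ALT at 3, 5 and 10 times ULN, and AST at the same multiples;
- bilirubin at 2 times ULN: "The counts and percentages of participants with a total bilirubin (TBL) measurement ≥2x the Covance ULN during the treatment period will be summarized";
- ALP at 2 times ULN.

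Each summary is split only by that analyte's own baseline. The maximum postbaseline value is also taken analyte by analyte.

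**The concern.** The protocol gives weight to the combination. On aminotransferase level alone, the condition is "ALT or AST >8x ULN" (or above 5 times ULN for more than two weeks). With bilirubin above 2 times ULN, an aminotransferase above 3 times ULN is enough. For ALP, the cut-off falls from 3 to 2.5 times ULN when bilirubin is raised. A reader of the hepatic safety results would therefore want to know how many participants in each arm showed the combination.

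Separate tables cannot answer that. Two isolated enzyme rises plus two isolated bilirubin rises in an arm give the same rows as two participants with both. What is at stake is how clearly the liver-safety result reads. The primary and key secondary analyses do not depend on it.

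**Working it through.** The plan states no figure to reproduce. The check is a reading of the planned outputs, followed by simple bounds.

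**1. Is the joint count planned anywhere?**

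| Output | Content | Links enzyme and bilirubin in one participant? |
|---|---|---|
| SAP 6.13.3.4.2 | ALT, AST, TBL, ALP thresholds, each alone | No |
| SAP 6.13.3.4.1 and Appendix 1 | Hepatic events by preferred term | No; rests on reported terms, not laboratory values |
| SAP 6.13.6 shift tables | Low/normal/high, per analyte | No |
| SAP 6.13.6 listing | Abnormal findings with arm, date and analyte | Only by hand |
| SAP 6.13.2 narratives | Deaths, SAEs, permanent discontinuations due to AEs and other named events | Case by case, for those participants only |
| Protocol 10.3.4.4.4 | Treatment-emergent abnormal/high/low percentages | No |

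The SAP names no by-arm output from the hepatic safety CRF described in Protocol Section 9.4.6.1.3.

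**2. Can the joint count be recovered from the planned rows?** Let *a* be the number in an arm above the enzyme cut-off, *b* the number above the bilirubin cut-off, and *n* = 70 (planned per arm). The joint count lies between max(0, *a* + *b* − 70) and min(*a*, *b*). The margins below are assumptions, because the documents give no expected rate.

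| *a*, *b* | Lower | Upper | Upper as % of 70 |
|---|---|---|---|
| 0, 3 | 0 | 0 | 0% |
| 1, 1 | 0 | 1 | 1/70 = 1.4% |
| 2, 1 | 0 | 1 | 1.4% |
| 2, 2 | 0 | 2 | 2/70 = 2.9% |

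Exact (Clopper-Pearson) 95% intervals are 0% to 5.1% for 0/70, 0.0% to 7.7% for 1/70, and 0.3% to 9.9% for 2/70.

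**3. Do the margins themselves match?** Not quite.

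- ALT and AST are tabulated separately, so the number with either one raised is known only to lie between the larger count and the sum of the two.
- There is no ALP row at 2.5 times ULN.
- The SAP cut-offs are inclusive, while those in Protocol 8.1.1 are strict. The planned rows can therefore only give an upper limit.

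**4. Are the data there?** Yes. Protocol Appendix 2 puts total bilirubin, ALT, AST and ALP in one chemistry panel. Scheduled postbaseline samples fall at Weeks 12, 24, 36, 44 and 52 and at the follow-up visit about four weeks later, plus any early discontinuation visit. Scheduled values of the four analytes thus share a sample. Section 9.4.6.1.1 adds repeats: abnormal tests "should be repeated within 48 to 72 hours to confirm the abnormality", and if the abnormality persists, "monitoring of symptoms and hepatic biochemical tests should be done at a frequency of 1 to 3 times weekly" at first, later every 1 to 2 weeks. A pairing window matters only when the enzyme and bilirubin peaks come from different draws.

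**The case against.** The strongest reply is that nothing was promised. The Protocol 8.1.1 conditions guide individual care and are not endpoints, and the SAP gives none of the eight a row of its own. It chose a different summary. That stands: a reader might infer that the SAP contradicts the protocol, but neither document commits to tabulating these conditions.

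Three further inferences also fail.

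- **That the thresholds could be picked after seeing the data.** Protocol 8.1.1 already fixes them. Only a rule for pairing values from different samples is open, and the need for that rule comes from the proposed table, not from the protocol.
- **That known Gilbert's syndrome leaves data uncollected.** The exemption removes the bilirubin route to the hepatic safety CRF. The proposed table uses central laboratory data, which are collected regardless, and other CRF routes remain.
- **That only these two conditions need values linked within a participant.** The two enzyme-plus-symptom conditions (which also name eosinophilia), the ALT rise relative to baseline, and the rise lasting more than two weeks need such links too.

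It is also fair that cases should be few. Screening excludes ALT above 3, ALP above 1.5 and bilirubin above 1.2 times ULN (known Gilbert's syndrome exempt for bilirubin). Serious cases, and those leading to permanent discontinuation due to an AE, get narratives, and a handful could be counted from the listing. SAP Section 6.2 permits extra analyses. None of this supplies a planned by-arm count, but it limits what is lost.

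**Conclusion.** The point holds as a minor improvement in method. No planned by-arm table shows the two enzyme-plus-bilirubin patterns, and the single-analyte rows cannot separate isolated from joint elevation when both margins are nonzero. If either margin is zero, the joint count is zero and nothing is lost for the bilirubin patterns; a zero bilirubin margin does not rule out the INR alternative in the first condition. With assumed margins of 2 and 2 in 70, the uncertainty is 0 to 2 participants, or 0% to 2.9%.

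The size rests on assumed margins and the planned 70 per arm. Percentages in the SAP use participants with a postbaseline value, so actual denominators may be smaller. Efficacy, alpha and power are unaffected.

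**What to change.** Add to SAP Section 6.13.3.4.2, by treatment and for both periods already stated there, counts and percentages of participants with postbaseline:

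1. ALT or AST above 3 times ULN and TBL above 2 times ULN;
2. ALP above 2.5 times ULN and TBL above 2 times ULN.

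Use the strict Protocol 8.1.1 cut-offs. Count a case when both values come from the same sample, or from samples within a window, in either order, that the sponsor fixes before unblinding. The retest intervals in Protocol Section 9.4.6.1.1 (72 hours up to two weeks, so 3 to 14 days) can inform its length, although they do not define an event.

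Show known Gilbert's syndrome separately, since Protocol 8.1.1 does not exempt it. Label row 1 as the bilirubin leg only: INR is not in the routine panel and is obtained only in the hepatic work-up. List joint cases with dates and INR where measured. A plot of maximum ALT or AST against maximum TBL is optional.

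The cost is some SAP wording, one table and one short listing from central laboratory data already collected, plus agreeing the window in advance. No new visits, samples or protocol change are needed.

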### 6.13.3.5. Hypoglycemia

The following categories in accordance with the 2019 American Diabetes Association position statement on glycemic targets (ADA 2019b) will be defined in the database.

#### **Glucose alert value (Level 1):**

- **Documented symptomatic hypoglycemia** is defined as any time a patient feels that he/she is experiencing symptoms and/or signs associated with hypoglycemia, and has a blood glucose (BG) level of <70 mg/dL (<3.9 mmol/L).
- **Documented asymptomatic hypoglycemia** is defined as any event not accompanied by typical symptoms of hypoglycemia, but with a measured BG <70 mg/dL (<3.9 mmol/L).
- **Documented unspecified hypoglycemia** is defined as any event with no information about symptoms of hypoglycemia available, but with a measured BG <70 mg/dL (<3.9 mmol/L).

### **Documented Clinically Significant Hypoglycemia (Level 2):**

- **Documented symptomatic hypoglycemia** is defined as any time a participant feels that he/she is experiencing symptoms and/or signs associated with hypoglycemia and has a BG level of <54 mg/dL (<3.0 mmol/L).
- **Documented asymptomatic hypoglycemia** is defined as any event not accompanied by typical symptoms of hypoglycemia but with a measured BG <54 mg/dL (<3.0 mmol/L).
- **Documented unspecified hypoglycemia** is defined as any event with no information about symptoms of hypoglycemia available but with a measured BG <54 mg/dL (<3.0 mmol/L).

## Severe Hypoglycemia (Level 3):

• Severe hypoglycemia is defined as an episode with severe cognitive impairment requiring the assistance of another person to actively administer carbohydrate, glucagon, or other resuscitative actions. These episodes may be associated with sufficient neuroglycopenia to induce seizure or coma. Plasma glucose measurements may not be available during such an event, but neurological recovery attributable to the restoration of PG to normal is considered sufficient evidence that the event was induced by a low PG concentration.

### **Other hypoglycemia categories:**

• Nocturnal hypoglycemia is defined as any hypoglycemic event that occurs between bedtime and waking.

If a hypoglycemic event meets the criteria of severe, the event would specifically be collected as an SAE. Serious hypoglycemia are defined by pharmacovigilance criteria and will also be captured with an SAE form.

To avoid duplicate reporting, all consecutive hypoglycemic events occurring within a 1-hour period will be considered to be a single hypoglycemic event.

Both the incidence (percent of patients experiencing  $\geq 1$  episode) and the rate (episodes/patient/year) of level 2 or level 3 hypoglycemia, and level 3 hypoglycemia will be reported by treatment group.

[figure not shown]
Severe/serious hypoglycemia will be considered as AESIs. The summaries of severe/serious hypoglycemia will be provided by treatment group. A listing of all events of severe hypoglycemia may be provided, if deemed necessary. This listing will provide treatment allocation, clinical characteristics of the hypoglycemic event, and concomitant antihyperglycemic medications.

## 6.13.3.6. Immunogenicity

## 6.13.3.6.1. Definitions of Sample ADA Status

At a high level, an individual sample is potentially examined multiple times, in a hierarchical procedure, to produce a sample anti-drug antibodies (ADA) assay result and potentially multiple cross-reactive antibodies assay results. The cut points used, the drug tolerance of each assay, and the possible values of titers are operating characteristics of the assay.

Figure GPIA. 6.2 details a flow chart that reflects the multitiered testing approach.

## Figure GPIA. 6.2 Flowchart of immunogenicity multitiered testing approach.

Abbreviations: ADA = anti-drug antibody; CP = cut point; GIP = glucose-dependent insulinotropic polypeptide; GIPR = glucose-dependent insulinotropic polypeptide receptor; GLP-1 = glucagon-like peptide-1; GLP-1R = glucagon-like peptide-1 receptor; LY = LY3298176; NAb = neutralizing antibodies.

Table GPIA.6.6 outlines the results as reported from Tier 2a of the multitiered testing approach.

Table GPIA.6.6.	Sample Anti-Drug Antibodies (ADA) Assay Results
-----------------	---

Sample Laboratory Result	Explanation
Detected	ADA are detected and confirmed.
Not Detected	The raw result as reported from the laboratory indicates not detected. The clinical interpretation of such results depends other factors (see Table GPIA.6.7).
NO TEST, QNS, etc	Sample exists but was unevaluable by the assay.

Abbreviations: ADA = anti-drug antibodies; QNS = quantity not sufficient.

It can be the case that the presence of high concentrations of tirzepatide will affect immunoassays, and conversely high levels of antibodies may affect the measurement of tirzepatide concentration. Thus, a tirzepatide drug concentration, assessed from a sample drawn at the same time as the ADA sample, plays a key role in clinical interpretation of a sample when the laboratory results are Not Detected (see Table GPIA.6.7).

Sample Clinical Interpretation	Explanation
ADA Present	ADA assay result is Detected
ADA Not Present	ADA assay result is Not Detected and simultaneous drug concentration is at a level that has been demonstrated to not interfere in the ADA detection method (ie, drug concentration is below the assay's drug tolerance level). For participants receiving placebo, drug concentration is not assessed and is assumed to be below the assay's drug tolerance level. If drug concentration was planned but is not available for a treatment-period sample, a Not Detected sample will be declared ADA Not present.
ADA Inconclusive	ADA assay result is Not Detected but drug concentration in the sample is at a level that can cause interference in the ADA detection method.
ADA Missing	ADA sample not drawn, QNS, not tested, etc., causing there to be no laboratory result reported or the result is reported as "no test."

 Table GPIA.6.7.
 Sample Clinical Anti-Drug Antibodies (ADA) Interpretation Results

Abbreviations: ADA = anti-drug antibodies; QNS = quantity not sufficient.

Similar terminology to Table GPIA.6.7 applies for each type of cross-reactive assay. Importantly, each of these are distinct assays and, in general, have different assay operating characteristics.

### 6.13.3.6.2. Definitions of Immunogenicity Assessment Periods

Immunogenicity Baseline Observations: Baseline period for immunogenicity assessment for each participant includes all observations on or prior to baseline visit. In instances where multiple baseline observations are collected, to determine participant ADA status the last nonmissing

immunogenicity assessment prior to first administration of study is used to determine treatmentemergent status (see below).

Immunogenicity Postbaseline Period Observations: Postbaseline period observations for each participant includes all observations after the first administration of study drug. There are two different periods listed below:

- The planned treatment period is defined as from the first dose of treatment to end of the treatment period
- The entire postbaseline period is defined as from the first dose of treatment to the end of safety follow-up visit or date of study withdrawal

